Study Protocol and Statistical Analysis Plan

Official Title:

The Effect of the Flipped Classroom Model on Nursing Students' Pediatric Pain Management Knowledge and Learning Motivation: A Randomized Controlled Trial (FLIPNURSE)

Unique Protocol ID:

ErsoyU-[name]-FC2022

NCT Number:

Pending (to be assigned)

Sponsor/Collaborators:

Faculty of Health Sciences, Burdur Mehmet Akif Ersoy University

Principal Investigator:

[name], Assistant Professor

Version/Date:

Version 1.0 — August 31, 2021

The Effect of the Flipped Classroom Model on Nursing Students' Pediatric Pain Management Knowledge and Learning Motivation: A Randomized Controlled Trial Abstract

Aim

The aim of this study is to evaluate the effect of the flipped classroom model on nursing students' knowledge level and learning motivation in pediatric pain management.

Background

Pain management in children is an important and multidimensional responsibility in nursing. However, the time allocated to pediatric pain and the opportunities for practical application in nursing education programs are limited. The integration of active learning approaches is necessary to increase knowledge and motivation in this area.

Design

This study is a parallel-group, randomized controlled experimental study conducted at a state university in Turkey.

Methods

A total of 84 third-year nursing students were randomly assigned to an intervention (n=42) and control (n=42) group. The intervention group was taught using the flipped classroom model, while the control group was taught using the self-directed learning model. Data were collected at three time points (pre-test, post-test, and 3 months post-intervention) and analyzed using a two-way mixed-design ANOVA.

Results

At baseline, there were no significant differences between the groups in terms of knowledge and motivation levels (p > 0.05). After the training, significant and sustainable increases were observed in both variables in the intervention group (p < 0.001), while no significant changes were observed in the control group.

The group × time interaction was found to be significant for both variables, indicating that the flipped classroom model provides an effective and sustainable contribution to knowledge level and motivation.

Conclusions

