However, a review of the literature reveals that no randomized controlled trial has yet been conducted to evaluate the effectiveness of the flipped classroom model in the field of pediatric pain management. Current systematic reviews and meta-analyses clearly emphasize that randomized controlled studies on the reverse class approach have primarily focused on general nursing practices or general pediatrics topics; no direct randomized controlled study specifically addressing pediatric pain management has been identified. (Barranquero-Herbosa, Abajas-Bustillo, & Drtego-Maté, 2022; Shi et al., 2025). This gap in the literature highlights the need for empirical studies evaluating the impact of pedagogical innovations in nursing education. This study aims to address this need by examining the effect of the flipped classroom model on nursing students' knowledge level and learning motivation in pediatric pain management.

Research Hypotheses

Hypothesis 1: The pediatric pain knowledge scores of students educated with the flipped classroom model are significantly higher than those of the control group.

Hypothesis 2: The learning motivation scores of students educated with the flipped classroom model are significantly higher than those of the control group.

2. Methods

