2.2.3. Motivation Questionnaire Regarding Teaching Materials

The Teaching Material Motivation Survey (ÖMMA) was developed by Keller and its validity and reliability were studied in Turkish by Kutu and Sözbilir (Keller, 2006; Kutu & Dir, Sözbilir, 2011). This scale, which aims to determine students' motivation levels toward instructional materials, consists of a total of 24 items on a 5-point Likert scale. The items in the attention-appropriateness dimension of the ÖMMA are 1, 2, 3, 4, 5, 6, 7, 8, 9, 10, and 11; while the items in the confidence-satisfaction dimension are 12, 13, 14, 15, 16, 17, 18, 19, 20, 21, 22, 23, and 24. Five items in the questionnaire (3, 12, 14, 16, 18) were reverse-coded. The minimum score in the questionnaire is 24, and the maximum score is 120. A high score on the survey indicates high motivation regarding the teaching material. The Cronbach's alpha coefficient is 0.83. In this study, the Cronbach's alpha value was found to be 0.789.

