3.3. Findings Related to Motivation Levels

Findings related to students' motivation levels are summarized in Table 3. There was no significant difference in motivation level scores between students in the intervention group and those in the control group in the pre-test (p > 0.05). However, when the results of the two-way mixed design ANOVA were examined, group effect (F=39.206, p < 0.001, η^2 =0.323), time effect (F=67.749, p<0.001, η^2 =0.452), and group*time interaction (F=70.240, p<0.001, η^2 =0.461) were found to be statistically significant. The significance of the group*time interaction indicates that the effect of the time factor on motivation levels is not the same for both groups (Table 3).

In the entrepreneurial group that received education with the flipped classroom model, a significant increase was observed in students' motivation scores. The average score, which was 83.61 ± 12.61 in the pre-test, increased to 120.66 ± 17.20 in the post-test and was recorded as 101.50 ± 12.26 in the retention test. The use of different letters (a, b, c) to denote the averages at different measurement times indicates statistically significant differences over time. In contrast, the motivation level scores of the control group, which received education using the self-learning model, remained quite close to each other at all time points, and no significant change was observed (pre-test: 86.76 ± 12.03 , post-test: 86.40 ± 11.91 , retention test: 85.61 ± 12.36). These findings indicate that the flipped classroom model is more effective than the self-directed learning model in enhancing students' motivation (Figure 2).

Table 3. Learning Motivation Scores of the Intervention and Control Groups

Motivation Survey Regarding Teaching	Intervention group (n=44) Mean (SD)	Control group (n=44) Mean (SD)	Statistic	Group	Time	Group*time interaction
Materials Pre-test	83.61 (12.61) ^a	86.76 (12.03) ^a	F	39,206	67,749	70,240
Post-test (4th week)	120.66 (17.20) ^b	86.40 (11.91) ^a	p	<0.001	<0.001	<0.001
Retention Test (3rd month)	101.50 (12.26)°	85.61 (12.36) ^a	η^2	0.323	0.452	0.461

a-c: Different letters indicate statistically significant groups within each column.

F: Two-way mixed design analysis of variance; η^2 , partial eta square; SD, standard deviation.

[figure not shown]

Figure 2. Mean Scores of Learning Motivation by Group and Time

4. Discussion

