The findings of this study suggest that the integration of the flipped classroom model into the pediatric nursing course has the potential to increase both students' knowledge levels and learning motivation. Especially in teaching topics that require clinical skills, using pedagogical approaches that prioritize student participation alongside traditional methods can support a more effective and lasting learning process.

The flipped classroom model can contribute to the development of students' higher-order cognitive skills, such as critical thinking, decision-making, and problem-solving, in the teaching of multidimensional and complex content such as pediatric pain management. In this regard, the model can guide nursing educators in reviewing their curricula, diversifying their teaching strategies, and integrating active learning-based approaches into their course content.

Furthermore, thanks to digital content support and remote access opportunities, the flipped classroom model has the potential to increase both academic achievement and intrinsic learning motivation by providing flexible learning environments tailored to students' individual learning speeds. This can contribute to strengthening student-centered and interaction-based learning experiences in nursing education.

6. Conclusion

This study revealed that the flipped classroom model significantly increased nursing students' knowledge levels regarding pediatric pain management and their learning motivation toward teaching materials in the short and medium terms. The findings emphasize the importance of integrating pedagogical approaches based on student-centered and active participation into nursing education, going beyond traditional teaching methods.

The flipped classroom model is an innovative teaching strategy that allows students to acquire theoretical knowledge at their own pace while allocating classroom time to deeper learning, discussion of clinical examples, and development of practical skills. In this regard, the model appears to be effective in teaching topics that require critical thinking and clinical decision-making skills, such as pediatric pain management.

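### The intervention group's post-test motivation mean (120.66, SD 17.20) exceeds the questionnaire's stated maximum of 120, so either the scores or the instrument description is wrong

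*Combined protocol and SAP*

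**What the plan says.** Section 2.2.3 says of the motivation questionnaire that it "consists of a total of 24 items on a 5-point Likert scale". It assigns items 1 to 11 to one dimension and items "12, 13, 14, 15, 16, 17, 18, 19, 20, 21, 22, 23, and 24" to the other, and gives the range: "The minimum score in the questionnaire is 24, and the maximum score is 120".

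Section 3.3 reports that the intervention group's mean "increased to 120.66 ± 17.20 in the post-test". Table 3 prints the same mean and SD. Nothing in the documents describes a rescaling, extra items or another version of the questionnaire.

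Motivation is the secondary outcome (section 2.8) and the subject of Hypothesis 2: "The learning motivation scores of students educated with the flipped classroom model are significantly higher than those of the control group". Section 6 concludes that the model raised students' knowledge and "their learning motivation toward teaching materials in the short and medium terms".

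Group size is also given in two ways. The abstract states: "A total of 84 third-year nursing students were randomly assigned to an intervention (n=42) and control (n=42) group". The column headings of Table 3 give 44 per group.

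**The concern.** A group mean above the highest score any student can obtain is impossible. With an SD of 17.20 around that mean, many individual totals would have to lie well above 120, so this is more than a 0.66-point rounding matter.

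The cell supplies the largest between-group contrast in the trial and drives the time and interaction effects for motivation. Until it is explained, a reader cannot tell whether the motivation effect is right, too large, or on a different scale from the one described.

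**Working it through.** **Inputs.** Section 2.2.3: 24 items, five-point responses. Section 3.3 and Table 3, means (SDs) at pre-test, post-test and retention: intervention 83.61 (12.61), 120.66 (17.20), 101.50 (12.26); control 86.76 (12.03), 86.40 (11.91), 85.61 (12.36). F values: group 39.206, time 67.749, interaction 70.240. Partial eta squared: 0.323, 0.452, 0.461.

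1. **Stated range.** The item lists give 11 + 13 = 24 items. Scored 1 to 5, totals run from 24 × 1 = 24 to 24 × 5 = 120. The stated range reproduces, and the reported mean is 0.66 above its top.

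2. **Highest mean compatible with the SD.** For scores between 24 and 120, (120 − m)(m − 24) ≥ SD² × (n − 1)/n. With SD 17.20 this gives m ≤ 116.89 for n = 42, and 116.89 also for n = 44. The printed mean is about 3.8 above that.

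3. **Group size behind the statistics.** Partial eta squared = F·df1/(F·df1 + df2). With 84 students (df2 = 82 and 164) the values are 0.3235, 0.4524 and 0.4614, as printed. With 88 they are 0.313, 0.441 and 0.450. The analysis therefore fits 42 per group, and the steps below use n = 42.

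4. **Did the value enter the ANOVA?** The time and interaction tests share one error term and have equal numerator degrees of freedom, so F(interaction)/F(time) = SS(interaction)/SS(time). Reported: 70.240/67.749 = 1.03677. From the printed means: 14,696.4/14,170.7 = 1.0371. With other post-test means and the remaining five unchanged:

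| Post-test mean | SS ratio |
|---|---|
| 120.66 (printed) | 1.0371 |
| 120.00 | 1.0391 |
| 116.66 | 1.051 |
| 110.66 | 1.085 |

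   Allowing for rounding or truncation of the other five means, the reported ratio solves to a post-test mean of 120.2 to 121.4.

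5. **Sharper version, assuming whole-number item scores.** Totals of 3512, 5068, 4263 (intervention) and 3644, 3629, 3596 (control) over 42 students give 83.619, 120.667, 101.500, 86.762, 86.405 and 85.619. All six match the printed means when cut to two decimals. Their SS ratio is 1.036765, against 1.036768 reported. Solving for the post-test total from the other five totals and the F ratio, without the printed 120.66, gives 5067.95 (5067.7 to 5068.2 for rounding of the F values). The maximum possible is 42 × 120 = 5040. The same method on the knowledge scores in Table 2 gives 1.19710, against 1.19711 reported.

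6. **SDs against F values in Table 3.** In balanced, complete data the cell variances and the two error terms must give the same error sum of squares.
   - From the SDs: 41 × (12.61² + 17.20² + 12.26² + 12.03² + 11.91² + 12.36²) = 42,824.
   - From the F values and means: (15,463.0/39.206) × 82 + (14,170.7/2/67.749) × 164 = 32,341 + 17,152 = 49,493.
   - The ratio is 1.156 (1.211 if n = 44). If the SDs and the time F are right, F(group) = 15,463.0/[(42,824 − 17,152)/82] ≈ 49.4, not 39.206.

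7. **Contrasts.** Post-test: 120.66 − 86.40 = 34.26. The stated maximum allows at most 120 − 86.40 = 33.6, or 116.89 − 86.40 = 30.5 if the SD is also right. Retention: 101.50 − 85.61 = 15.89, with standard error √[(12.26² + 12.36²)/42] = 2.686, so t = 5.92 on 82 df and the 95% CI is 10.5 to 21.2.

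**The case against.** The contradiction itself is hard to dispute, but its reach can be.

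- **The SD and F mismatch is not specific to motivation.** Table 2 fails the same identity in the other direction: its SDs give 94,151 and its F values and means require 85,640, a ratio of 0.910. This stands. The mismatch is a reason to rerun the tables, but it says nothing about the 120.66 cell in particular.
- **The 116.9 ceiling and the 30.5-point limit depend on an SD that the same table puts in doubt.** This also stands. Without the SD, the excess is 0.66 and the contrast is at most 33.6 points. All these limits assume that the stated range is right.
- **The ratio test separates 120.00 from 120.66 only narrowly (1.0391 against 1.0371).** From the printed means alone, the low end of the solution clears 120 by less than 0.2. The tighter total of about 5068 needs whole-number scores and truncated means. Both readings still lie above the maximum.
- **Hypothesis 2 names no time point, and the retention contrast supports it without this cell.** The other five means lie within range. This limits the direct damage to the post-test contrast and the ANOVA that includes it. It does not establish that the retention scores are sound, because they come from the same instrument and scoring.
- **The primary outcome is not touched.** The knowledge means lie within that scale's range of 29 to 145.

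**Conclusion.** The concern holds. The reported mean is impossible under the instrument as described, by 0.66 points from the range alone and by about 3.8 points if the SD of 17.20 is correct. The F ratio indicates that the value was analysed, so a single mistyped digit is an unlikely explanation. That inference assumes balanced, complete data with 42 per group; the solved total also assumes whole-number item scores.

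The documents do not show which side is wrong. If section 2.2.3 misdescribes the questionnaire, the scores could be valid, but Table 3 would still need correction because its SDs and F values disagree by 15.6% and its headings give the wrong n for its statistics. No corrected mean can be derived from the documents, and nothing here shows that the motivation effect is absent. The short-term motivation conclusion cannot be relied on as reported, and this must be resolved before it is used.

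**What to change.** 1. Return to the item-level export of the online forms. Check every item and total, for all students and all three visits, against the range of the questionnaire actually used, including the five reverse-coded items.
2. If section 2.2.3 is wrong, correct its item count or range, and confirm that both groups received the same version at every visit. If scores are wrong, re-score them.
3. Rerun Table 3, correct its group-size headings, and check that the SDs and F values agree.
4. Restate the motivation conclusion with the post-test and retention contrasts given separately, each with a confidence interval.

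The cost is a range check plus either a text correction or re-scoring, and a rerun on existing data. The motivation effect may shrink or may stand.

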4.1. The Effect of the Flipped Classroom Model on Pediatric Pain Knowledge Level

A statistically significant and sustained increase in the knowledge levels of nursing students regarding pediatric pain management was observed in those who received education through the flipped classroom model. In particular, the high scores in the retention test compared to the pre-test level indicate the sustainability of learning in the long term. This can be attributed to the flipped classroom model's structure, which encourages active student participation, and its provision of application-based learning environments (Liu et al., 2018; Xu et al., 2019).

These results are consistent with the existing literature. The flipped classroom approach has been shown to enhance knowledge levels in nursing and medical education through various studies (Betihavas et al., 2016; Barranquero-Herbosa, Abajas-Bustillo, & Ortego-Maté, 2022; Merrou et al., 2023). Especially in clinical and applied fields, this model, supported by case analyses, problem-based learning, and group discussions, is reported to enable students not only to acquire knowledge but also to develop their abilities to analyze, evaluate, and transfer knowledge (Liu et al., 2018; Xu et al., 2019; Merrou et al., 2023; Alshehri, Levett-Jones, & Pich, 2024).

The learning gains in question are not limited to quantitative increases in knowledge but also reflect cognitive depth. In this context, the findings can also be evaluated within the framework of Bloom's cognitive domain taxonomy. The flipped classroom model contributes to the activation of higher-order cognitive processes such as analysis, synthesis, and evaluation

beyond the levels of knowledge and comprehension (). Similarly, in a study by Paralikar et al. (2022), it was noted that students who participated in the flipped classroom model showed significant development in Bloom's higher cognitive levels and achieved success, particularly in the application and analysis levels. It is stated that this model facilitates students' access to basic knowledge through offline preparation and reinforces their knowledge with higher-order thinking skills in an interactive classroom environment (Paralikar et al., 2022).

In addition to these comprehensive cognitive contributions, the uniqueness of the study area is also noteworthy. The limited number of studies evaluating the effectiveness of the flipped classroom model in narrow and clinically critical areas such as pediatric pain management using a randomized controlled design increases the contribution of the findings to the literature.

The findings indicate that the flipped classroom approach is more effective than the traditional self-learning model in terms of increasing and maintaining knowledge levels in both the short and long term. This result shows that active classroom interaction and practical work carried out after the pre-learning process contribute positively to the retention of learning. Indeed, studies conducted by Sáiz-Manzanares et al. (2020) also emphasize that learning environments with high levels of active participation have a significant impact on knowledge retention (Sáiz-Manzanares et al., 2020).

However, some limitations of this model have also been noted in the literature. In particular, it has been pointed out that factors such as difficulty in accessing digital materials and insufficient assumption of individual learning responsibility may negatively affect student motivation (Busebai & John, 2021). However, in this study, maintaining a strong technical infrastructure and ensuring high accessibility of the digital platform used minimized such negative effects and supported the effectiveness of the learning process.

4.2. The Effect of the Flipped Classroom Model on Learning Motivation

Statistically significant increases in the motivation levels of students who received education through the flipped classroom model were recorded in both the short and long term. In contrast, no significant change in motivation scores was observed in the control group where the self-directed learning model was applied. These findings indicate that the flipped classroom approach is effective in increasing students' interest in the material, encouraging active participation in class, and supporting intrinsic motivation.

In the literature, the positive effect of the flipped classroom model on learning motivation is supported by various studies. According to systematic reviews and meta-analyses conducted by Betihavas et al. (2016) and Liu et al. (2018), flipped classroom models have been found to have significant positive effects on learning motivation, autonomy, and self-efficacy (). In particular,

applications supported by case-based and problem-focused learning methods are noted to more effectively engage students in the learning process and enhance motivation (Merrou et al., 2023).

However, studies also highlight that this positive effect on motivation is not always sustainable. Some findings have revealed that the flipped classroom model creates high motivation among students in the initial stage, but motivation decreases over time when digital content is presented in an uninteractive, repetitive, or inadequate manner (Lo & Emp; Hew, 2019; Betihavas et al., 2016). This situation demonstrates that not only the structure of the learning model but also the quality of the content presented and the level of interaction are decisive factors in the sustainability of motivation.

Among the key factors that enable motivation to be sustained in the long term are the timeliness of content, diversity of applications, active participation of students in the learning process, and quality of interaction with instructors (Chen et al., 2014; Martin et al., 2020). Indeed, in this study, the fact that motivation scores remained high even in the retention test compared to the initial level suggests that the pedagogical quality of the content design and the intensity of interaction in the learning environment played a supportive role in motivation.

5. Nursing Education Implications

The findings of this study suggest that the integration of the flipped classroom model into the pediatric nursing course has the potential to increase both students' knowledge levels and learning motivation. Especially in teaching topics that require clinical skills, using pedagogical approaches that prioritize student participation alongside traditional methods can support a more effective and lasting learning process.

The flipped classroom model can contribute to the development of students' higher-order cognitive skills, such as critical thinking, decision-making, and problem-solving, in the teaching of multidimensional and complex content such as pediatric pain management. In this regard, the model can guide nursing educators in reviewing their curricula, diversifying their teaching strategies, and integrating active learning-based approaches into their course content.

Furthermore, thanks to digital content support and remote access opportunities, the flipped classroom model has the potential to increase both academic achievement and intrinsic learning motivation by providing flexible learning environments tailored to students' individual learning speeds. This can contribute to strengthening student-centered and interaction-based learning experiences in nursing education.

6. Conclusion

This study revealed that the flipped classroom model significantly increased nursing students' knowledge levels regarding pediatric pain management and their learning motivation toward teaching materials in the short and medium terms. The findings emphasize the importance of integrating pedagogical approaches based on student-centered and active participation into nursing education, going beyond traditional teaching methods.

The flipped classroom model is an innovative teaching strategy that allows students to acquire theoretical knowledge at their own pace while allocating classroom time to deeper learning, discussion of clinical examples, and development of practical skills. In this regard, the model appears to be effective in teaching topics that require critical thinking and clinical decision-making skills, such as pediatric pain management.

The use of this approach in practice-based courses such as pediatric nursing can positively influence not only students' knowledge levels but also their motivation and attitudes toward learning. In this regard, giving more space to innovative learning approaches such as the flipped classroom model in nursing curricula will contribute to the development of students' academic achievements as well as their clinical competence after graduation.

Future research focusing on evaluating the long-term effects of the flipped classroom model in different nursing courses and examining its outcomes on students with different learning profiles will contribute to strengthening evidence-based data on the model's effectiveness.

7. Limitations and strengths

One of the prominent strengths of this study is its randomized controlled experimental design, which was structured to test the research hypotheses. The statistical similarity of the intervention and control groups in terms of their initial descriptive characteristics increased the internal validity of the group comparisons. The validity and reliability of the measurement tools used have been previously reported, supporting the quality of the data obtained. The intervention protocol was structured, developed based on expert opinions, and implemented with equal content and duration for both groups. The use of two different digital platforms (epediatri.com and UZEM) to minimize contamination risk was supported by careful planning of synchronization and access timing. Additionally, the statistical analyses were conducted by an independent expert, and the study results were reported in accordance with the CONSORT 2010 () checklist, which are among the factors enhancing the methodological strength of the study.

On the other hand, the study has some limitations. The fact that the research was conducted at a single center and included only nursing students from one university limits the generalizability

of the findings to other institutions or samples. The inability to ensure participant and practitioner blinding may increase the risk of observational bias; however, the fact that the analysis process was conducted blind by an independent statistician partially mitigates this limitation. The fact that learning outcomes were assessed solely using self-report scales, without being supported by behavioral or performance-based objective measures, narrows the scope of the study's evaluation. Additionally, the sustainability assessment covered only a three-month period, so data on long-term effects could not be obtained. The sample consisting solely of third-grade students also prevented comparisons of the model's effects across different grade levels.

Despite these limitations, the study's experimental design, intervention implementation integrity, measures taken to control for bias, and high reporting quality demonstrate that the research was conducted at a methodologically robust and reliable level.

Funding resources

This study was not funded by any public institution, private sector organization, or civil society organization. The research process was conducted within the framework of the researchers' personal academic efforts and institutional resources.

CRediT authorship contribution statement

[name]: Writing – review & editing, Writing – original draft, Resources, Methodology, Investigation, Formal analysis, Data curation, Conceptualization.

[name]: Writing – review & editing, Validation, Supervision, Project administration, Methodology, Investigation, Formal analysis.

Declaration of generative AI and AI-assisted technologies in the writing process

While preparing this work, the author(s) used ChatGPT (GPT-4) to enhance the manuscript's language clarity and readability. After using this tool, the author(s) reviewed and edited the content as needed and take(s) full responsibility for the publication's content.

Declaration of Competing Interest

All authors declare that they have no financial or personal relationships that could inappropriately influence or bias their work. Specifically, none of the authors have potential conflicts of interest, such as employment, consultancies, stock ownership, honoraria, paid expert testimony, patent applications, or grants.

Protocol

The full protocol is not publicly available but can be obtained upon reasonable request.

Acknowledgments

